## **5. INVESTIGATIONAL MEDICINAL PRODUCTS**

### **5.1. Randomization, Blinding and Treatment Codes**

Randomization to GS-5745 or placebo will be based on a randomization schedule prepared by Gilead and/or a designee before the start of the study. Eligible subjects will be randomized via an interactive web response system (IWRS). As described in Section 8.5.1, randomization will be stratified by ECOG status (0 or 1) at screening, geographic region (Latin America or other participating countries), and primary tumor site (gastric or GEJ).

The IWRS will be used to maintain a central log documenting screening, to implement randomization, to assess current inventories of study drug, to initiate any necessary resupply of study drug, and to document discontinuation of the study drug.

The IWRS will assign kit numbers and provide instructions for dispensing of blinded study drug (GS-5745/placebo). It is anticipated that subjects will usually begin study drug immediately after randomization.

#### **5.1.1. Procedures for Breaking Treatment Codes**

In the event of a medical emergency where breaking the blind is required to provide medical care to the subject, the investigator may obtain treatment assignment directly from the IWRS system for that subject. Gilead recommends but does not require that the investigator contact the Gilead medical monitor before breaking the blind. Treatment assignment should remain blinded unless that knowledge is necessary to determine subject emergency medical care. The rationale for unblinding must be clearly explained in source documentation and on the electronic case report form (eCRF), along with the date on which the treatment assignment was obtained. The investigator is requested to contact the Gilead medical monitor promptly in case of any treatment unblinding.

Blinding of study treatment is critical to the integrity of this clinical trial and therefore, if a subject's treatment assignment is disclosed to the investigator, the subject will have study treatment discontinued. All subjects will be followed until study completion unless consent to do so is specifically withdrawn by the subject.

Gilead Drug Safety and Public Health (DSPH) may independently unblind cases for expedited reporting of suspected unexpected serious adverse reactions (SUSARs).

### **5.2. Description and Handling of Study Treatments**

#### **5.2.1. Formulation**

##### **5.2.1.1. GS-5745**

GS-5745 is formulated as a sterile, aqueous buffered solution containing acetate at pH 5.0, with sucrose and polysorbate 20 added for stabilization. Each 10 mL vial contains 400 mg GS-5745 at a concentration of 40 mg/mL.

#### 5.2.1.2. Placebo to Match GS-5745

Placebo to match GS-5745 is formulated as a sterile, aqueous buffered solution containing acetate at pH 5.0, with sucrose and polysorbate 20 added for stabilization in a 10 mL vial.

#### 5.2.1.3. mFOLFOX6

The mFOLFOX6 dosing regimen will consist of *dl*-LV or *l*-LV, oxaliplatin and 5-FU.

##### 5.2.1.3.1. *dl*-Leucovorin and *l*-Leucovorin

*dl*-Leucovorin and *l*-LV are commercially sourced. Information regarding the formulation can be found in the current prescribing information.

##### 5.2.1.3.2. Oxaliplatin

Oxaliplatin is commercially sourced. Information regarding the formulation can be found in the current prescribing information.

##### 5.2.1.3.3. 5-Fluorouracil

5-Fluorouracil is commercially sourced. Information regarding the formulation can be found in the current prescribing information.

### 5.2.2. Packaging and Labeling

Study drug (GS-5745/placebo) solution will be supplied in 10 mL glass vials with coated elastomeric stoppers and aluminum crimp overseals with a flip-off cap.

Study drug(s) to be distributed to centers in the US and other participating countries shall be labeled to meet applicable requirements of the United States Food and Drug Administration (FDA), European Union (EU) guideline to Good Manufacturing Practice - Annex 13 (investigational medicinal Product(s)), and/or other local requirements. Gilead or designated distribution depots will distribute study drug vials to sites as per current Good Manufacturing Practices (cGMP) requirements.

mFOLFOX6 will be supplied by Gilead per local country regulations.

### 5.2.3. Storage and Handling

Study drug (GS-5745/placebo) should be stored at 2 - 8 °C. Storage conditions are specified on the study drug label. Until dispensed to the subject, all study drug should be stored in a securely locked area, accessible only to authorized site personnel. To ensure stability and proper identification, the study drug should be stored in the containers in which they were supplied until dosing to the subject.

Components of mFOLFOX6 regimen are commercially sourced. Information regarding the storage and handling of *dl*-LV/*l*-LV, oxaliplatin and 5-FU can be found in the current prescribing information.

### 5.3. Dosage and Administration of Study Drug and mFOLFOX6

Study drug (GS-5745/placebo) will be administered 800 mg via intravenous infusion over approximately 30 ( $\pm$  5) minutes at the research clinic by a qualified staff member on Days 1 and 15 of each 28-day treatment cycle of mFOLFOX6. One cycle of mFOLFOX6 consists of 2 infusions. mFOLFOX6 will be administered immediately following study drug on Days 1 and 15 of each cycle as well. After 6 cycles of mFOLFOX6, the oxaliplatin component will be discontinued. Leucovorin and 5-FU will be continued as maintenance therapy, in combination with GS-5745/placebo, in the absence of disease progression or toxicity warranting discontinuation of therapy. The mFOLFOX6 dosing regimen will consist of *l*-LV 200 mg/m^2 or *dl*-LV 400 mg/m^2 and oxaliplatin 85 mg/m^2 followed by bolus 5-FU 400 mg/m^2 and a 46-hour infusion of 5-FU 2400 mg/m^2. Minor modifications to the duration of the infusion time are permitted as per institutional standard. Adjustments to the dose of mFOLFOX6 are permitted in response to treatment emergent adverse events. Refer to the local prescribing information for care of subjects including contraindications, subject monitoring, and the medicinal products prohibited or to be used with care for all the components of mFOLFOX6.

The Investigator or a qualified designee must be present during the administration of GS-5745/placebo. Subjects should be observed following end of infusion and discharged at the discretion of the Investigator or qualified designee.

Documentation of the study drug and mFOLFOX6 administration will be noted on the eCRF and in the source documentation.

#### 5.3.1. Dose Interruption and Reduction

If an adverse event is attributed to only 1 drug (ie, GS-5745/placebo or 1 or more component of mFOLFOX6), the investigator's discretion will be used to determine if the drug(s) not attributed to the adverse event will be withheld based on the investigator's assessment of risk-benefit of withholding 1 or more drugs (please see sections 5.3.1.1 and 5.3.1.2 for additional guidance).

Careful monitoring must be ensured for subjects with a history of allergic reactions to other platinum based chemotherapy agents. In the event of anaphylactic shock symptoms, interrupt infusion immediately and initiate appropriate treatment. Resumption of oxaliplatin treatment following anaphylactic reaction is contraindicated.

Clinically significant, abnormal 12-lead safety ECGs should be repeated. Subjects who have 2 consecutive ECGs showing a new absolute QTc duration > 500 msec, or a QT/QTc > 60 msec over the corresponding baseline value must discontinue any medications that could prolong the QT interval (including oxaliplatin). Subject's concomitant medications should be reviewed to determine a potential etiology for the ECG changes. Appropriate intervention (ie cardiology evaluation, telemetry monitoring, management of electrolyte abnormalities) in response to treatment emergent QT interval prolongation should be initiated.

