### **6.2.6. Electrocardiogram Assessment**

A single 12-lead electrocardiogram (ECG) will be collected at Screening, Day 1 of each cycle, at the EOT and EOS visits, per standard practice. Additional ECGs following administration of oxaliplatin will be collected at visits when oxaliplatin is administered after the infusion is completed (i.e., Days 1 and 15 of each cycle, up to a maximum of six 28-day cycles) as required per country label guidance regarding cardiac monitoring. The investigator will review all ECGs and retain the tracing with the source documents. ECGs obtained after oxaliplatin infusions must be reviewed by the investigator/sub investigator before subjects leave the clinic/infusion center.

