- s End of treatment (EOT) assessments will be completed only by subjects who discontinue all treatment prior to disease progression. These assessments should be completed as soon as possible after the decision is made. Every attempt should be made to keep the subject in the study and continue to perform tumor evaluation by CT or MRI every 8 weeks until disease progression.
- t End of study (EOS) assessments will be completed when the subject meets at least 1 of the criteria for study discontinuation (Section 3.6).
- u The 30-day safety follow up visit will be performed following the last dose of GS-5745/placebo, or all components mFOLFOX6, whichever is discontinued later.
- v The 55-day safety follow up phone visit will be performed following the last dose of GS-5745/placebo, or all components mFOLFOX6, whichever is discontinued later.
- w A single 12-lead electrocardiogram (ECG) will be collected at Screening, Day 1 of each cycle, and at the EOT and EOS visits, per standard practice. Additional ECGs following administration of oxaliplatin will be collected at visits when oxaliplatin is administered after the infusion is completed (i.e., Days 1 and 15 of each cycle, up to a maximum of six 28-day cycles) as required per country label guidance regarding cardiac monitoring.

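### Protocol Section 5.3.1 makes stopping oxaliplatin mandatory only after two consecutive ECGs with QT prolongation, but does not date the repeat ECG or hold oxaliplatin until it is read

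*Protocol*

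**What the plan says.** The stop rule is in the ECG paragraph of Protocol Section 5.3.1. It applies to "Subjects who have 2 consecutive ECGs showing a new absolute QTc duration" above 500 msec, or a QT/QTc more than 60 msec above baseline. Such subjects "must discontinue any medications that could prolong the QT interval (including oxaliplatin".

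For the first abnormal tracing, the section says that "Clinically significant, abnormal 12-lead safety ECGs should be repeated". It then asks for a review of concomitant medications and adds: "Appropriate intervention (ie cardiology evaluation, telemetry monitoring, management of electrolyte abnormalities) in response to treatment emergent QT interval prolongation should be initiated".

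The ECG schedule is in Section 6.2.6: "A single 12-lead electrocardiogram (ECG) will be collected at Screening, Day 1 of each cycle", and at the end-of-treatment and end-of-study visits. The Appendix 2 footnote adds: "Additional ECGs following administration of oxaliplatin will be collected at visits when oxaliplatin is administered after the infusion is completed". Both places qualify these extra tracings in the same way: "as required per country label guidance regarding cardiac monitoring". Section 6.2.6 also states: "ECGs obtained after oxaliplatin infusions must be reviewed by the investigator/sub investigator before subjects leave the clinic/infusion center". That duty covers only the post-oxaliplatin tracings. The ECG row of the Appendix 2 table marks both Day 1 and Day 15 of each cycle.

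**The concern.** Asking for confirmation before permanently stopping an active drug is reasonable, because one QTc reading can be wrong. The gap is the interval before confirmation. The mandatory stop depends on a second ECG that has no date, and nothing written suspends oxaliplatin while that ECG is outstanding.

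The protocol itself treats QT as an oxaliplatin risk. It excludes long QT and low potassium, magnesium or calcium at entry (Section 4.3), asks for care with QT-lengthening drugs during oxaliplatin (Section 5.4), and names oxaliplatin in the stop rule. A subject with one reading above 500 msec could nevertheless be infused again without any departure from the protocol text. This is a patient-safety point. It does not touch alpha, power, event counts or the efficacy analysis.

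**Working it through.** **Step 1: is a hold or a deadline written anywhere else?**

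- Section 5.3.1.1 postpones treatment after Grade 3 or worse toxicity, but only GS-5745/placebo and only for toxicity attributed to it.
- Appendix 5, Appendix Table 1 has no QT row. Its row for other non-hematologic events keeps the dose at Grades 1 and 2 and lowers the responsible drug one level at Grades 3 and 4. Neither is a hold. By contrast, the respiratory row suspends oxaliplatin while interstitial lung disease is excluded, and the neutrophil and platelet rows hold treatment at the start of a cycle.
- Section 7.5 requires an abnormal ECG to be recorded as an adverse event when signs or symptoms accompany it. A symptom-free QTc finding may therefore never reach the adverse-event rules.
- Section 7.6 gives a repeat target, preferably 3 calendar days, for laboratory abnormalities but not for ECGs.
- Section 6.9 permits an unscheduled ECG but does not require one.
- SAP Section 7.5.2 tabulates QTcF categories and sets no dosing rule.

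No other section supplies either rule.

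**Step 2: how many infusions can fall before the second ECG?**

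Inputs: oxaliplatin 85 mg/m² on Days 1 and 15 of six 28-day cycles (Sections 3.1 and 5.3), and the ECG schedule above. The plan's own total is reproduced: 2 × 6 = 12 infusions, as in the synopsis. The documents give no figure for infusions between two ECGs, so it is counted here as the number of infusions after the first ECG and before the next scheduled one. Days are nominal; the ±3-day visit windows are ignored.

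| ECGs collected | First ECG, then next scheduled ECG | Infusions between |
|---|---|---|
| Day 1 only | after dose, then before next Day 1 dose | 1 |
| Day 1 only | before dose, then before next Day 1 dose | 2 |
| Day 1 only | after dose, then after next Day 1 dose | 2 |
| Day 1 only | before dose, then after next Day 1 dose | 3 |
| Days 1 and 15 (Appendix 2 table, literal) | same timing at both visits | 1 |
| Days 1 and 15 (Appendix 2 table, literal) | Day 1 before dose, then Day 15 after dose | 2 |
| Days 1 and 15 (Appendix 2 table, literal) | Day 15 after dose, then next Day 1 before dose | 0 |
| Day 1 pre-dose plus label-required post-infusion | Day 1 before, then Day 1 after | 1 |
| Day 1 pre-dose plus label-required post-infusion | Day 1 after, then Day 15 after | 1 |
| Day 1 pre-dose plus label-required post-infusion | Day 15 after, then next Day 1 before | 0 |

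At the starting dose:

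- 1 infusion is 85 mg/m², 1/12 = 8.3% of the planned infusions.
- 2 infusions are 2 × 85 = 170 mg/m², 2/12 = 16.7%.
- 3 infusions are 3 × 85 = 255 mg/m², 3/12 = 25%.

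If the repeat is done before the next infusion, the count is 0 in every row.

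**Step 3: what would close the gap?**

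A hold until the repeat is read gives 0 in every row. A 3-day deadline alone gives 0 after a post-infusion ECG, because infusions are 14 days apart. After a pre-dose Day 1 ECG it still allows that day's infusion (1). The hold matters more than the deadline.

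**The case against.** The strongest reply is that an instruction to repeat an abnormal ECG naturally means an extra tracing prompted by the finding, since the next scheduled one would be taken anyway. On that reading the count is usually 0. This stands, and it is why no infusion count can be given without its conditions.

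Several safeguards also exist:

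- The opening of Section 5.3.1 gives the investigator discretion over drugs not blamed for an event, which suggests that the blamed drug is withheld.
- The listed interventions follow treatment-emergent QT prolongation and carry no two-ECG condition.
- Section 7.6 brings toxicities to the medical monitor.
- Section 5.3 refers sites to local prescribing information, which the documents do not reproduce and which may contain a hold.
- Appendix Table 1 is only a recommendation, so its missing QT row does not direct anyone to dose.

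All of this lowers the risk. None of it is a written hold or a dated repeat, and the study plans about 188 centers with ECG practice that varies by country label.

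A reader might infer that the schedule leads to two further infusions after a first reading above 500 msec. The documents do not support that. The figure needs the repeat to wait for the next scheduled visit, ECGs on Day 1 only, and the same pre- or post-dose timing each time. Nor is two a ceiling, because a pre-dose ECG followed by a post-dose ECG gives three.

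**Conclusion.** The concern holds as a gap in a safety rule. The mandatory stop needs two consecutive qualifying ECGs, the repeat has no deadline, oxaliplatin is not held meanwhile, and the Day 1 ECG is not timed against dosing. A site can follow the protocol text and still give oxaliplatin after one qualifying ECG.

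The exposure is 0 infusions with a prompt repeat. If the repeat waits for the next scheduled ECG, it is:

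- 0 to 1 with label-required post-infusion ECGs;
- 1 on a literal reading of the Appendix 2 table with consistent timing, and at most 2 with mixed timing;
- 1 to 3 with Day 1 ECGs only.

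This rests on nominal visit days and on the protocol text alone; local prescribing information may be stricter. The documents give no rate of QT events, so no number of affected subjects is claimed. Confirmed prolongation is already covered by the existing rule. The change is worth making because it is cheap; nothing in the analysis plan depends on it.

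**What to change.** Add to Section 5.3.1: *After any single ECG meeting either QT criterion, hold oxaliplatin and repeat the ECG before any further oxaliplatin is given; resume only if the repeat does not meet the criterion, and discontinue oxaliplatin if it does.* State in Section 6.2.6 that the Day 1 ECG is taken and read before oxaliplatin.

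Two additions are optional: a deadline for the repeat (the same visit, or the 3 calendar days of Section 7.6, for the sponsor's clinicians to confirm) and a row in Appendix Table 1 pointing to Section 5.3.1.

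The cost is a few sentences at the next amendment and an occasional infusion delayed by a repeat ECG. Sample size and the efficacy analysis do not change.

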5.3.1.1. GS-5745/Placebo (Study Drug)

If a subject experiences a Grade 3 or greater toxicity considered secondary to study drug (GS-5745/placebo), treatment will be postponed until the toxicity returns to Grade 0-1 (as defined by NCI CTCAE v 4.03) or returns to the subject's baseline value. If the toxicity returns to Grade 0-1 or the subject's baseline value, the subject may resume GS-5745 at the originally assigned dose level.

If the event does not resolve to Grade 0-1 or the subject's baseline within 28 days, treatment with study drug (GS-5745/placebo) must be permanently discontinued. If the subject experiences a recurrence of the Grade 3 or greater toxicity after restarting study drug, treatment with GS-5745/placebo will be discontinued. Subjects who permanently discontinue treatment with study drug (GS-5745/placebo) may continue treatment with mFOLFOX6 after consultation with the medical monitor.

Subjects who are not receiving any chemotherapy (mFOLFOX6) should not receive study drug (GS-5745/placebo) as monotherapy. Investigators should contact the Gilead Medical Monitor with any questions regarding study drug dose modification, interruption or discontinuation.

5.3.1.2. mFOLFOX6

Recommended dose reduction for the components of mFOLFOX6 is described in [Table 5-1](#) and is based on the adverse event (AE) table described in [Appendix 5](#). Sites may also follow their institutional practice for dose reductions. Leucovorin doses may be adjusted per institutional guidelines in the event of a supply shortage.

Subjects who interrupt all components of mFOLFOX6 for greater than 28 days secondary to drug toxicity(s) that do not resolve should permanently discontinue all study treatment.

Subjects who permanently discontinue all components of mFOLFOX6 should also discontinue GS-5745/placebo.

Investigators should contact the Gilead Medical Monitor with any questions regarding study drug dose modification, interruption or discontinuation.

**Table 5-1. Dose Reduction Levelsa for mFOLFOX6**

Drug	Dose Level		
	Starting Dose	-1	-2 b
Oxaliplatin	85 mg/m 	65 mg/m 	50 mg/m 
5-FU bolus	400 mg/m 	OMIT	OMIT
5-FU continuous infusion over 46-48 hours	2400 mg/m 	1900 mg/m 	1500 mg/m 
dl-Leucovorin/l-Leucovorin c	400/200 mg/m 	100%	100%

- a If an AE is believed likely to be due to 1 drug, it is permissible to decrease dose of that drug only.
- b Further dose levels (-3, -4, etc.) will be 20% dose reductions from the previous level for oxaliplatin and 5-FU continuous infusion. In addition, the bolus dose of 5-FU will continue to be omitted, and the leucovorin dose will remain unadjusted (100%).
- c Dosing of leucovorin will remain fixed at 100% of recommended dose.

#### **5.4. Prior and Concomitant Medications**

During the course of the clinical trial, study subjects are anticipated to continue the use of prescribed medications identified during the screening procedures, consistent with study inclusion and exclusion criteria.

Non-study anticancer chemotherapy or immunotherapy (approved or investigational) are not permitted during the trial. If administered, the subject may be removed from the trial.

Concomitant medications that are known to lengthen QTc interval must be used carefully while the subject is receiving oxaliplatin. Please refer to <https://www.crediblemeds.org/> for a listing of such medications.

#### **5.5. Accountability for Study Drug**

The investigator or designee (eg, pharmacist) is responsible for ensuring adequate accountability of all used and unused investigational medicinal product during the study. This includes acknowledgement of receipt of each shipment of study drug (quantity and condition) and tracking of vials assigned/utilized for subject dosing.

Study drug (GS-5745/placebo) accountability records will be provided to each study site to:

- Record the date received and quantity of study drug vials
- Record the date, subject number, subject initials, the vial number dispensed
- Record the date, quantity of used and unused vials returned, along with the initials of the person recording the information.

Dispensing records will include the initials of the person dispensing the study drug or supplies.

##### **5.5.1. Investigational Medicinal Product & mFOLFOX6 Return or Disposal**

The study drug and mFOLFOX6 should be disposed of at the site as per local standard operating procedures. Please see Section 9.1.7 for additional instructions.

## 6. STUDY PROCEDURES

The study procedures to be conducted for each subject enrolled in the study are presented in tabular form in [Appendix 2](#) and described in the text that follows.

The investigator must document any deviation from protocol procedures and notify the sponsor or contract research organization (CRO).

Safety and tolerability assessments will include regular monitoring of AEs, changes from baseline in laboratory variables, physical examinations, vital signs, and special safety assessment like ECGs.

From the time of obtaining informed consent through the first administration of study drug, record all serious adverse events (SAEs), as well as any non-serious AEs related to protocol-mandated procedures on the AEs eCRF. All other untoward medical occurrences observed during the Screening period, including exacerbation or changes in medical history are to be captured on the medical history eCRF.

